8.4 Definition of a Serious Adverse Event (SAE)

An SAE is any adverse event that results in any of the following outcomes: □ death,
$\ \square$ a life-threatening event (at risk of death at the time of the event),
$\hfill \Box$ requires in patient hospitalization or prolongation of existing hospitalization,
$\hfill\Box$ a persistent or significant disability/incapacity, or
$\hfill \square$ a congenital anomaly/birth defect in the offspring of a subject.
Important medical events that may not result in death, be life-threatening, or require hospitalization may be considered a serious adverse event when, based upon appropriate medical judgment, they may jeopardize the subject and may require medical or surgical intervention to prevent one of the outcomes listed in this definition.

A distinction should be drawn between serious and severe AEs. A severe AE is a major event of its type. A severe AE does not necessarily need to be considered serious. For example, nausea which persists for several hours may be considered severe nausea, but

would not be considered serious. On the other hand, a stroke that results in only a limited degree of disability may be considered a mild stroke, but would be considered serious. We will use the Clavien-Dindo Classification system [47], as well as the Comprehensive Complication Index (based off of the Clavien-Dindo system) [48] to classify and analyze patient adverse events. Grade III (a/b), Grade IV (a/b), and Grade V events will be considered SAEs. (See Appendix 1 for classification table)

8.4.1 Relationship of AE/SAE to study intervention or device

The relationship of each Event to the study intervention should be characterized using one of the following terms in accordance with NEMOURS IRB Guidelines: **definitely, probably, possibly, unlikely or unrelated**. In this case, the "study intervention" in considered to be the surgical intervention and implantation of the medical device (*Anterior vertebral body tethering surgery under general anesthesia with spinal cord monitoring*). This includes (but is not limited to) induction of anesthesia, incision and surgical approach, device implantation, and recovery. **For each SAE, the PI and Safety Officer will make a case-by-case determination on the relationship of the SAE to the study procedure, which will be documented in the study documents.**

There will be further classification of the Event as either "device-related", "not device-related", or "uncertain to be device-related". Device-related adverse events are those events directly related to the integrity, safety, or biomechanics of the implanted device. This can include variables like device breakage or device migration. Other adverse events which are considered not device-related are those that are related to the act of the surgery and medical recovery (anesthesia, incision and surgical approach, post-operative recovery, etc.). This distinction will be indicated in the study documents. For each Event, the PI and Safety Officer will make a case-by-case determination on whether the Event is "device related", "not device related", or "uncertain". An event which is classified as "device related" will be considered an Adverse Device Effect. Adverse device effects have special reporting guidelines, as outlined below.

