moderate scoliosis in patients with remaining growth is to utilize a thoracolumbosacral orthosis (TLSO brace) to prevent progression of deformity. The scientific evidence has supported the efficacy of this intervention in avoiding progression of the Cobb angle to 50 degrees or more.

If treated with a TLSO brace, many idiopathic scoliosis patients would conceivably be subjected to years of brace wear and the cost and psychological factors inherent therein. Additional downsides of brace treatment include the potentially negative psychosocial impact of wearing an external sign of deformity during adolescence, a key period of emotional development. Prior research has identified negative psychosocial effects related to wearing a brace in children.

Recent evidence has suggested that certain curve patterns will likely progress to 50 degrees or more, despite treatment with a TLSO brace. Sanders, et al. demonstrated a correlation of Cobb angle (greater than 35 degrees) and skeletal maturity (bone age 4 or less) to the risk of progression to 50 degrees or more, despite TLSO bracing. The evidence supports that the current practice of TLSO bracing is not an effective treatment to avoid progression to 50 degrees in these patients. It is on this population (thoracic Cobb angle greater than 35 degrees, bone age of 4 or less) that we intend to test the safety and efficacy of Anterior Vertebral Body Tethering to avoid curve progression to more than 50 degrees.

Objectives:

The objectives of this study are to assess the safety and efficacy of Anterior Vertebral Body Tethering Surgery (AVBT) to treat Idiopathic Scoliosis.

Study Design:

This is a Phase II, non-randomized, open label study of the anterior insertion of a Polyethylene Terephthalate (PET) cord in pediatric scoliosis. The study will be conducted at a single site-Nemours – Alfred I duPont hospital for Children

Setting/Participants:

This is a single-site, Sponsor-Investigator led phase II clinical trial of Vertebral Body Tethering for pediatric idiopathic scoliosis in children aged 8-16 years. The study will have a retrospective arm to collect data from patients who had the tether surgery prior to approval of the prospective study.

Study Interventions and Measures:

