- 2) Post-operative active phase: Incidence of infection (within 90 days post-op), pneumothorax, bronpulmonary plug, or any reportable SAE.
- 3) Extended follow-up phase: Incidence of over-correction, implant failure (measured on serial x-ray), incidence of curve progression to >50 degrees at 5 year follow-up, or incidence of secondary surgery or re-operation to correct further spine deformity (not related to trauma or other issues not related to the initial surgery / disease).

Statistical And Analytic Plan

Cobb angle is a continuous variable. T-test or repeated measures Anova will be used to detect any change in Cobb angle post-operatively. Linear regression will be utilized to assess which variables are associated with change in post-operative Cobb angle.

DATA AND SAFETY MONITORING PLAN

The PI and Data Safety group will meet regularly to discuss any safety events. Group's reports will be forwarded to the IRB during continuing review per ORC monitoring guidance. Safety reporting will be according to IRB SOP 408 and governing FDA guidelines. The PI and study team will also comply with all ORC monitoring standards. The PI will meet with the study team regularly to discuss study progress and ensure data fidelity. The first meeting will take place before initiation of the study to discuss the protocol and establish guidelines to monitor the study. The Sponsor-PI will work in conjunction with the DSMB members to prepare an agenda to address the review of the initiation of the trial, reporting of adverse events, stopping rules, etc.

Meetings will be held before enrolling the 1st, 5th, 9th and so forth patient. If a Serious Adverse Event (SAE) occurs, a separate meeting will be held.

The meetings will be held at the Nemours AIDHC Department of Orthopedics using WebEx connectivity for attendees who are not in the office.

Meeting minutes will be recorded by the study coordinator and will become part of the study binder.

DSMB group includes the following members who do not have a financial or other types of conflict of interest related to this study:

- 1. [name] [name]
- 2. [name]
- 3. [name], [name]

[name] will not lead the DSMB meetings, but help to prepare reports/events for the DSMB. [name] will be present as a participant in the meetings to answer questions by the DSMB personnel, but will not be present for a closed portion of the meeting.

Members of the DSMB are:

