6.5 Interim Analysis

The study team will perform interim analyses based on the stopping rules listed in section 6.6 (below). If any of these rules are met, the study will halt enrollment until appropriate measures can be put in place to reduce patient risk. All reporting of AE/SAEs during the study will adhere to the guidelines in Section 8 (Safety Management).

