9.3 Regulatory and Ethical Considerations

9.3.1 Data and Safety Monitoring Plan

The PI will monitor data and safety throughout the duration of the study and will report any adverse events in accordance with IRB policies. The PI, Safety Monitor, and study team will perform interim safety analyses as outlined in Section 6.6. Safety monitoring will be handled internally by the study Safety Monitor and NEMOURS Office of Research Compliance (ORC). We will also submit reports to the FDA, device manufacturer, or both as per medical device reporting requirements specified in 21CFR803.

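### The PI shares the relatedness call and the study team applies the stopping rules, while the DSMB that already meets after any SAE has no stated decision role

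*Combined protocol and SAP*

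**What the plan says.** The abstract describes a "single-site, Sponsor-Investigator led phase II clinical trial", open label and with one cohort.

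- **Classification (8.4.1).** For relation to the procedure, "the PI and Safety Officer will make a case-by-case determination on the relationship of the SAE to the study procedure". For relation to the device, again "the PI and Safety Officer will make a case-by-case determination on whether the Event is" device-related, not device-related or uncertain.
- **What the rules count.** 6.6.1 covers SAEs related to the study procedure: all of the first 5 patients, 7 of the first 10, or more than 50% after 20 cases. 6.6.2 covers device-related SAEs, using defined events (screw failure, tether failure, implant re-operation).
- **Who applies them.** In 6.5, "The study team will perform interim analyses based on the stopping rules listed in section 6.6", and a met rule halts enrollment until risk-reducing measures are in place. In 9.3.1, "The PI, Safety Monitor, and study team will perform interim safety analyses as outlined in Section 6.6", and "Safety monitoring will be handled internally by the study Safety Monitor and NEMOURS Office of Research Compliance (ORC").
- **The DSMB.** The Data and Safety Monitoring Plan after the synopsis sets up a DSMB whose members are declared free of conflicts of interest. It meets before the 1st, 5th, 9th and later patients, its meetings have a closed portion, and stopping rules are among its agenda items. Further, "If a Serious Adverse Event (SAE) occurs, a separate meeting will be held".

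Sections 6.5, 8.4.1 and 9.3.1 do not mention the DSMB.

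**The concern.** A stopping rule that counts only related events is as independent as the person who decides relatedness. Here the PI, who leads the study as sponsor-investigator, shares that decision, and the PI and study team then apply the rule to the resulting count. The DSMB is the body suited to checking both steps, and it is already convened at the right moment, but the plan gives it no authority over either.

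The protocol leaves room for judgment. 8.4.1 uses five causality grades, and 6.6.1 does not say which of them count as related. 8.4.1 also allows an uncertain device category, and 6.6.2 does not say how that is counted. Device-related covers cord, staples, set screws and vertebral screws in 5.2, but only the cord in 6.3.2. No bad faith is needed: honest borderline calls that lean one way are enough.

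At stake are the halt on enrolling further children for an investigational combination of implants, and the device-related incidence that 6.3.2 reports with an exact 95% interval.

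**Working it through.** The plan gives no error rate or operating characteristic for its stopping rules (6.4 states that there is no power analysis), so there is no figure of its own to reproduce.

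**Step 1. Who decides what**

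| Decision | Assigned to | DSMB role in available text |
|---|---|---|
| Relation of SAE to procedure | PI and Safety Officer (8.4.1) | none stated |
| Relation of event to device | PI and Safety Officer (8.4.1) | none stated |
| Whether a 6.6 rule is met | Study team (6.5); PI, Safety Monitor and study team (9.3.1) | stopping rules are an agenda item |
| Halting and resuming enrollment | No decision-maker named (6.5) | none stated |

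**Step 2. How close the limits are**

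One patient's SAE reclassified as unrelated turns a met limit into a missed one: 5/5 becomes 4/5, 7/10 becomes 6/10, and 11/20 (55%) becomes 10/20 (50%, not above 50%).

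**Step 3. Effect on the chance of a halt under 6.6.1**

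Inputs from the plan: the three limits above and a total of 30 subjects (3.3.2). Assumptions not in the documents: the true proportion p of patients with a procedure-related SAE, the share m of these called unrelated, independence between patients, each patient's SAE status known at each look, and up to 30 operated patients. As 30 covers both the retrospective and prospective arms, the prospective number may be smaller.

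Counted rate: q = p(1 − m).

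Single looks for p = 0.6:
- m = 0, q = 0.60: P(X ≥ 7 of 10) = 0.382; P(X ≥ 11 of 20) = 0.755.
- m = 0.1, q = 0.54: 0.245 and 0.556.
- m = 0.2, q = 0.48: 0.141 and 0.343.

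The rule has several looks, so the relevant quantity is the chance of ever meeting it. An exact binomial recursion adds one patient at a time and removes the paths that stop: at 5/5, at 7 or more of 10, or at more than n/2 for each n from 20 to 30. Starting the last look at 21 rather than 20 changes nothing, because 11/20 implies at least 11/21, which still exceeds 50%.

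Chance of ever meeting 6.6.1 by 30 patients:

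| True rate p | m = 0 | m = 10% | m = 20% | m = 30% |
|---|---|---|---|---|
| 30% | 4.1% | 1.9% | 0.8% | 0.3% |
| 50% | 62.5% | 42.5% | 24.3% | 11.3% |
| 60% | 91.2% | 76.6% | 54.6% | 31.1% |
| 70% | 99.3% | 95.3% | 82.5% | 58.5% |

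The absolute loss at m = 20% is largest at the middle rates: 62.5 − 24.3 = 38.2 points at 50%, and 91.2 − 54.6 = 36.6 points at 60%. At 30% it is 4.1 − 0.8 = 3.3 points.

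**The case against.** The other side has several good points.

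- **The PI does not decide alone.** The call is shared with a Safety Officer. The DSMB membership list is not in the available text, so that person may sit on the DSMB. A reader might infer that the party under review controls the count, but the documents do not establish this. They show that the PI shares the call and that no independence is stated for the other half.
- **The monitoring is not confined to the study team.** 9.3.1 also names the Safety Monitor and the Office of Research Compliance. DSMB reports go to the IRB, and 8.6 sets IRB reporting times for on-site SAEs. This is real oversight, but none of it is a stated review of relatedness or a decision on 6.6.
- **The sections do not flatly contradict each other.** The monitoring plan never gives the DSMB these decisions, so there are no two rival assignments. The DSMB's role is undefined where the sections meet, and they need reconciling.
- **Discretion is limited in places.** 8.4.1 defines the study intervention broadly, from anesthesia to recovery, so few perioperative SAEs could plausibly be called unrelated. 6.6.2 uses defined events. This narrows the scope, most clearly for the device rules. It does not settle later SAEs or which causality grades count under 6.6.1.
- **The primary endpoint is not filtered by relatedness.** A reader might infer that tilted calls lower the primary rate. They do not: 6.1 takes the overall AE/SAE rate, and the recording plan in section 8 captures all AEs to day 90 and all SAEs afterwards whatever their cause. Only late non-serious AEs depend on the call. They lie outside the immediate post-operative period of the primary objective and enter no stopping rule.
- **The size depends on assumed rates.** This is correct. At a true rate of 30% the rule is rarely met even with perfect classification.

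**Conclusion.** The concern holds as a gap in who decides. The PI shares the relatedness call, both families of stopping rules count only events so classified, and the PI, Safety Monitor and study team apply them. The conflict-free DSMB, already meeting after any SAE, has no stated right over either step.

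If one in five related SAEs is called unrelated, the chance of ever meeting 6.6.1 by 30 patients falls by about 37 to 38 percentage points at true rates of 50% to 60%, by 16.8 points at 70% (99.3 − 82.5), and by about 3 points at 30%. These rates and shares are assumptions. The conclusion about roles rests on the text alone.

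The consequence is a missed or delayed enrollment halt and a lower reported device-related incidence. A reader might take a met rule to end the trial, but 6.5 halts enrollment only. Nothing in the documents suggests that calls have been or would be made in bad faith. The change is worth making because the independent body already exists.

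**What to change.** 1. In 8.4.1, have the DSMB confirm or overrule the relatedness call, to procedure and to device, for every SAE at the meeting already required after an SAE. The PI and Safety Officer still make the first assessment.
2. In 6.5 and 9.3.1, state that the DSMB, in closed session, determines whether a 6.6 rule is met and whether enrollment halts or resumes. The study team and Safety Monitor prepare the data.
3. Align the Data and Safety Monitoring Plan after the synopsis with these sections so that all four give the same account.

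The cost is protocol wording and longer DSMB meetings. No new body or extra SAE data collection is needed, because all SAEs are already recorded regardless of cause. The change should stop at SAEs: non-serious events after day 90 that are judged not device-related are not recorded under the present plan, so reviewing them would require new data collection.

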8.4 Recording plan for AE / SAEs

Surgery and Post-operative Phase (Day 0 – POD 90):

For these phases, all AEs (including SAEs) will be noted in the study records and reported per IRB and FDA requirements outlined below. The subjects will be encouraged to contact the office with any concerns, and the medical record will be monitored by study staff for indications of AEs.

Extended Follow-up Phase (POD 91-POD 1825):

For this phase, all SAEs will be recorded (regardless of cause). Only AEs which are deemed "device related" will be recorded on study documents and reported per IRB and FDA requirements outlined below. The subjects will still be encouraged to contact the office with any concerns, and the medical record will be monitored by study staff for indications of SAEs or device-related AEs.

Only the AE/SAEs indicated above will be recorded in a patient-specific study binder, kept in the secure Orthopedics research office. The binder will contain a full description of the event, including the nature, date and time of onset, determination of non-serious versus serious, intensity (mild, moderate, severe), duration, causality, and outcome of the event. Hard copies of the primary documents (medical record notes) describing the event and any associated treatment will be printed and kept in the patient-specific study binder. A redundant copy of adverse events will be kept in the study REDCap database and will be maintained by the study team separately from the patient-specific study binder. The study binder will serve as the official record of all Events.

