5.2 Safety Evaluation

Subject safety will be monitored by recording all AEs and SAEs, and will be recorded on the complication form in the patient's study binder. The evaluation of safety is a primary objective of

this research study. There will be a clear classification of "device-related" adverse events. Device-related adverse events are those events directly related to the integrity, safety, or biomechanics of the device components: **PET cord, staples, set screws and vertebral screws.** This can include variables like device breakage or device migration. Other adverse events which are considered not device-related are those that are related to the act of surgery and medical recovery. The type of events will be documented on the CRF.

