6.3.2 Safety Analysis

The safety endpoint will be factors associated with the adverse events in patients that have undergone Anterior VBT Surgery. Variable reporting for adverse event will be dichotomous. Descriptive statistics will be used to report number and type of adverse events. Further, chi-square or fisher-exact test analysis will be used to identify variables that correlate with adverse events following anterior tethering surgery. Further, logistic regression will be conducted to clarify which variables are associated with adverse outcomes. Odds ratio along with confidence intervals will be reported.

All subjects will begin the safety analysis at Study Day 0 (day of surgery). Intraoperative and post-intervention medical events or signs and symptoms of the complications arising after the start of study intervention will be captured using list of common events associated with Anterior VBT Surgery. Adverse signs, symptoms, and/or laboratory abnormalities already existing prior to the baseline visit will be captured in the medical history assessment.

The date of onset, severity, and end date (if relevant) will be documented.

Medical events resulting from any procedure performed in the study will be collected as adverse events (AEs). The event description, date of onset, end date, severity, and outcome will be documented for the study-related AEs. The frequencies of AEs by type, body system, severity and relationship to study intervention will be summarized. SAEs (if any) will be described in detail. A distinction will be made between those AE/SAEs which are "device-related", those which are "not device-related", and those which are "uncertain to be related". "Device-related" complications will include any events directly related to the integrity, safety, or biomechanics of the PET cord. Device-related AE incidence will be summarized along with the corresponding exact binomial 95% two-sided confidence intervals. 22

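### After POD 90 the recording rule omits non-serious AEs of uncertain device-relatedness, so a class the safety analysis promises to report is incomplete

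*Combined protocol and SAP*

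**What the plan says.** **Classification.** Section 8.4.1 (Relationship of AE/SAE to study intervention or device) states: "There will be further classification of the Event as either 'device-related', 'not device-related', or 'uncertain to be device-related". It applies to every event: "For each Event, the PI and Safety Officer will make a case-by-case determination on whether the Event is 'device related', 'not device related', or 'uncertain". Section 6.3.2 carries the same split into the analysis. Alongside device-related events it distinguishes "those which are 'not device-related', and those which are 'uncertain to be related".

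**Recording.** The rule in section 8.4 (Recording plan for AE / SAEs) depends on the phase.

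- Day 0 to POD 90: "For these phases, all AEs (including SAEs) will be noted in the study records".
- POD 91 to POD 1825, serious events: "For this phase, all SAEs will be recorded (regardless of cause".
- POD 91 to POD 1825, other events: "Only AEs which are deemed 'device related' will be recorded on study documents".

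The section then limits the study binder to the events it has just listed and names the binder as the official record.

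**General statement.** Section 5.2 has no phase limit: "Subject safety will be monitored by recording all AEs and SAEs, and will be recorded on the complication form in the patient's study binder".

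**Analysis.** Section 6.3.2 plans one interval estimate on this point: "Device-related AE incidence will be summarized along with the corresponding exact binomial 95% two-sided confidence intervals". Section 6.1 makes the rate of AEs/SAEs the primary endpoint and gives no time window.

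**Seriousness.** Clavien-Dindo grades I and II are AEs (section 8.3). Grades III to V, and events meeting the usual seriousness criteria, are SAEs (section 8.4, Definition of a Serious Adverse Event).

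**The concern.** An uncertain class is useful only if its events are kept, so that they can be tabulated, reclassified when more is known, or counted in a worst-case analysis. Here the class exists throughout, but its non-serious members stop being recorded at POD 90.

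That cut-off coincides with the period in which the protocol looks for device problems. Section 6.6.2 diagnoses tether failure only after 3 months, and the synopsis places over-correction and implant failure in the extended follow-up phase. Late device problems can also be non-serious under the plan's own terms. In section 6.6.2, tether failure is an SAE only if it is noted before maturity and the overall Cobb angle has worsened. Loosened screws or staples count as screw failure only if re-operation is needed. Keeping all SAEs therefore does not cover every late event for which attribution is in doubt.

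Safety is the primary objective, so a gap in the AE record matters more here than it would in an efficacy trial.

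**Working it through.** The plan states no AE rate and no power calculation, so there is no figure to reproduce. The check is mainly a comparison of texts.

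**Step 1. What each rule keeps.** Under the recording plan:

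| Event | Day 0 to POD 90 | POD 91 to POD 1825 |
|---|---|---|
| SAE, any class | recorded | recorded |
| Non-serious, device-related | recorded | recorded |
| Non-serious, uncertain | recorded | **not recorded** |
| Non-serious, not device-related | recorded | not recorded |

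Under section 5.2 every cell would read recorded. The two instructions concern the same binder and cannot both be followed after POD 90. Section 6.3.2 plans its three-way distinction without a phase limit, so it needs entries that the recording plan excludes.

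**Step 2. How long the gap lasts.** POD 91 to 1825 is 1825 − 91 + 1 = 1735 days. Day 0 to POD 1825 is 1826 days. 1735 / 1826 = 0.950, or 95.0% of planned follow-up, ignoring visit windows and dropout.

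**Step 3. Effect on device-related incidence.** Section 6.3.2 counts only the device-related class. Recording uncertain events would not by itself change that figure. It changes only if some of them are reclassified, or if a second figure includes them.

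Let k of N subjects have a recorded device-related AE. Let u further subjects have only an unrecorded uncertain event that was in truth device-related. The reported incidence is k/N, the true incidence is (k + u)/N, and the shortfall is u/N. Section 3.3.2 gives a total of 30 subjects across both arms, so each such subject costs 1/30 = 3.3 percentage points.

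**Step 4. Illustration.** The values of k and u are assumptions; the documents give neither. Take k = 3 and N = 30. For x = k + u subjects, the exact binomial (Clopper-Pearson) limits are the 0.025 quantile of Beta(x, N − x + 1) and the 0.975 quantile of Beta(x + 1, N − x).

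| u | Incidence if u were known | Exact 95% CI |
|---|---|---|
| 0 | 3/30 = 10.0% | 2.1% to 26.5% |
| 1 | 4/30 = 13.3% | 3.8% to 30.7% |
| 2 | 5/30 = 16.7% | 5.6% to 34.7% |
| 3 | 6/30 = 20.0% | 7.7% to 38.6% |

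In each row the plan would report the u = 0 line. If none of the uncertain events was device-related, that line is correct.

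**Step 5. Is there a route back?** The follow-up report provision in section 8 covers SAEs only. No section says how the class of a non-serious AE is to be updated.

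**The case against.** A reader might infer that uncertain events are never captured and that device-related incidence is therefore biased downward beyond repair. The documents do not support this, for four reasons.

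- **The gap is narrow.** All AEs to POD 90 and all SAEs to POD 1825 are recorded whatever their class. Section 8.2 also sends notable non-serious AEs that could involve risk to the IRB at continuing review, without a phase limit.
- **A device failure found later is itself recordable.** Suppose back pain of unclear cause is followed by a film showing that the cord has lost tension. The film finding is either an SAE under section 6.6.2 or a device-related AE. If incidence is counted per subject, that subject is counted. What is lost is the first sign and its onset date.
- **The chart survives.** Sections 4.4.1 to 4.4.6 schedule record, x-ray and complications review at each extended visit, and section 4.5 covers unscheduled visits. The recording plan sets no deadline for deeming an event device-related.
- **The main safety questions are partly protected.** Section 2.1 ties the primary objective to the immediate post-operative period, when everything is recorded. The extended-phase endpoints in the synopsis are radiographic or surgical.

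All four points stand and limit the concern, but they do not remove it. Recovery from the chart would be unplanned and possibly selective, and an IRB narrative is not a tabulated class. A subject whose cause is never confirmed stays out of the record. The primary endpoint in section 6.1 is not confined to the early phase, and the contradiction with section 5.2 remains.

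**Conclusion.** The concern holds as a gap and a contradiction in the recording rule. From POD 91 to POD 1825, about 95% of planned follow-up, non-serious AEs classed as uncertain do not enter the official record. Sections 5.2, 6.3.2 and 8.4.1 all imply that they should. This much rests on the text alone.

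Two consequences are firm. The uncertain category and the overall AE rate are incomplete after POD 90 and cannot be compared with the earlier phase. No sensitivity analysis from the study record can show whether device-related incidence is affected.

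Understatement of that incidence is a possibility, not a finding. It requires that some unrecorded uncertain events were truly device-related, in subjects not otherwise counted. If so, the size is 3.3 percentage points per subject with N = 30; the number of such subjects cannot be derived from the documents.

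**What to change.** 1. In the POD 91 to POD 1825 rule of section 8.4 (Recording plan), record non-serious AEs classed as device-related or as uncertain to be device-related, and extend the chart-monitoring sentence to match.
2. State that the class may be updated when later films are read, keeping the initial class and the date of change.
3. Reconcile section 5.2 with this rule. Non-serious AEs classed as not device-related would still go unrecorded after POD 90, so section 6.3.2 should present the overall AE rate by phase and say what each phase includes.
4. In section 6.3.2, report device-related AE incidence with its exact 95% interval twice: device-related only, and device-related plus uncertain.

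The cost is protocol wording and a few more AE entries, drawn from complications reviews already scheduled at the extended visits. No procedure or visit is added. The second incidence figure may be higher than the first, and the report would have to explain the difference.
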